1.1.12 Rationale for QTc Objective

In this study, the effect of BMS-986158 on the QT interval will be evaluated. Preclinical evaluations did not identify a signal indicating that BMS-986158 may increase the QT interval or affect cardiac conduction. Similar to other drugs in this class, the likelihood BMS-986158 directly or indirectly affects QTc intervals is low. Despite the low risk, such evaluation is required during the development of a therapeutic agent and the design of this study treating subjects across several doses is well suited for this type of evaluation. Serial electrocardiograms (ECGs) (reviewed by a central laboratory) will be collected with matching PK samples from all subjects in dose escalation and at least 20 subjects treated at the MTD or an alternative selected dose in the dose expansion monotherapy cohorts.

ES is a rare disease in adults and mostly affects children and adolescents, with a peak of incidence around 15 years.²⁰⁴ Clinically, most pediatric patients present with lesions arising from the bone, whereas more than 50% of lesions in adults occur in the soft tissue.²⁰⁵ Early observations suggested an adverse prognosis for patients of older age,²⁰⁶ whereas recent findings report no effect of age on OS.²⁰⁷ The lower dose intensity of chemotherapy used to treat adults was discussed as a possible factor.²⁰⁵ Currently, the treatment of adult patients follows the same principles as for ES in the pediatric age group.^{208,209} Approximately 20% to 25% of ES patients are diagnosed with metastatic disease, and with current multimodality treatments, including chemotherapy and radiation, 5-year survival in this patient population is less than 20%.²⁰⁹ During the dose escalation part of this study, 1 subject with ES responded to BMS-986158 treatment with improved clinical symptoms, including reduced pain and increased overall activity. This observation supports previously published findings that BET inhibitors may affect survival of ES cells in preclinical models.⁶³

During the dose expansion part of this study, BMS-986158 will initially be tested in subjects with TNBC, CRPC, DHL, non-GC-DLBCL, NMC and possibly other advanced cancers, including UM, RCC, NSCLC, and BL in the Subsequent Expansion. Except for BL, these cancers are rare in children.^{204,210,211,212,213} BL is the most common (approximately 46%) non-Hodgkin's lymphoma in children and adolescents in western countries, and rare in adults with approximately 1,200 cases per year in the US.^{214,215} A recent study reported that 5-year relative survival in BL for children. adults, and the elderly were 90.4%, 47.8%, and 28.9%, respectively. Some predictors of poor outcome were shared among all age groups, such as multiple primary tumor sites and advanced stage disease.²¹⁶ It was suggested that older patients have inferior outcomes compared with younger patients due to the low intensity therapy, and one of the ways to reduce treatment burden, especially in elderly patients, might be the use of targeted therapy approaches.^{214,215} In both adults and children, relapse occurs infrequently but is characterized by a poor prognosis. Pediatric patients who relapse or progress have chemotherapy-resistant disease and can rarely be cured.^{217,218,219} In adults, relapsed or refractory BL treated with salvage therapy resulted in median OS of 2.8 months.²²⁰ Because patient numbers are low, there are no randomized trials comparing different relapse regimens. These results provide rationale for development of alternative treatment approaches focusing on targeted therapy to circumvent chemotherapy-resistant disease by providing alternative therapeutic targets across different ages.

Current experience with BMS-986158 (see Section 1.4.4 and the Investigator's Brochure for details) did not identify drug-related adverse events (AEs) that warrant exclusion of adolescent subjects from this study. Thus, the balance of benefit to risk may be favorable in adolescent subjects with advanced cancers and poor treatment options. Therefore, adolescent subjects with NMC, BL, or ES will be eligible to participate in this study. Additional indications will be allowed at the discretion of the Sponsor if the tumor contains similar genetic abnormalities sensitive to regulation by the BET family proteins.

Rationale for Adolescent Dose

BMS-986158

Analysis of available PK data indicates dose proportionality and a linear relationship between exposure and body size, allowing for appropriate scaling of dose to younger subjects using allometric scaling of clearance and volume. Current experience with BMS-986158 demonstrates that tested doses are safe in adult subjects. To provide an additional margin of safety, the lower limit of enrollment will be 12 years of age. By 6 years of age, developmental processes related to drug disposition are typically complete, and body weight is the main factor differentiating pediatric and adult drug exposures.^{221,222,223} The PK results suggest that BMS-986158 exposure in adolescent subjects \geq 40 kg could be similar to adults at the same dose level. Therefore, adolescent subjects \geq 40 kg will be administered the same doses as adults and receive a starting dose of 4.5 mg for 2 weeks (10 doses) followed by 3.75 mg for the remainder of treatment in Schedule A. Due to the limited PK data collected in Part 1, only adolescents \geq 40 kg will be enrolled in Part 2. By enrolling subjects \geq 40 kg, it is expected that around 50% of adolescents will be eligible.

Nivolumab

Flat doses of nivolumab, 360 mg Q3W or 480 mg Q4W, have been shown to be safe and efficacious in adult subjects. In adolescent subjects, 6 mg/kg dose Q4W up to a maximum of 480 mg will be used for the Schedule A dose expansion. The combination of BMS-986158 with nivolumab will only be pursued if results of the effect of BMS-986158 monotherapy in the tumor microenvironment is favorable for the combination.

1.2 Research Hypothesis

There is no formal primary research hypothesis for this study to be statistically tested. It is anticipated that BMS-986158 as monotherapy and/or in combination with nivolumab will demonstrate adequate safety and tolerability at pharmacologically relevant doses, so as to permit further clinical development (at a recommended dose range).

1.3 Objectives(s)

1.3.1 *Primary Objectives*

- To assess the safety and tolerability and to assess the DLTs, MTD, and recommended Phase 2 dose (RP2D) of BMS-986158 as monotherapy for subjects with advanced solid tumors and hematologic malignancies.
- If combination with nivolumab is pursued, to assess the safety and tolerability at the RP2D of BMS-986158 in combination with nivolumab and to assess the DLT for subjects with advanced solid tumors and hematologic malignancies.

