of whom were evaluable for DLT. No DLTs were observed through DL4 (80 mg OD). Reversible grade 4 thrombocytopenia was the DLT at DL4 BID (40 mg x2) and 120 mg OD continuous. Sixteen patients experienced Grade 3-4 thrombocytopenia and 3 patients had grade 3-4 neutropenia. Grade 3 non-hematologic toxicities were diarrhea, vomiting, hyperglycemia, and hypernatremia (1 patient each). Other toxicities were non-cumulative grade 1-2 gastrointestinal events (8 patients with diarrhea, 3 dysgueusia, 2 vomiting, 1 nausea, 1 anorexia, 1 abdominal pain), hyperglycemia (7 patients), skin rash (3 patients), asymptomatic coagulation factor VII decrease (2 patients), and direct bilirubin increase (1 patient). Clinically relevant activity was reported in 6 patients treated from 40 to 120 mg, including one CR (120 mg, 17+ weeks [wks]) and 1 PR (80 mg, 28 wks), both in DLBCL patients failing 3-4 prior therapy lines, and both with clinical benefit. Four other patients (two with DLBCL, one follicular, and one lymphoplasmacytic lymphoma) had minor tumor shrinkage with clinical benefit (40 mg, 36+ wks; 80 mg, 14 wks; 120 mg 15 wks; 120 mg, 17 wks). Similarly, a study using another BET inhibitor, CPI-0610, as monotherapy reported objective clinical responses in 5 of 36 subjects with relapsed or refractory DLBCL, specifically in T cell/histocyte-rich and activated B-cell subtypes. Of note was 1 CR and 2 PR in subjects with ABC-DLBCL, 1 PR in follicular lymphoma, and 1 PR in T-cell histocyte rich lymphoma.⁷⁷

The initial assessment of the risk of side effects of BMS-986158 in clinical trials was based on data from nonclinical toxicology studies in rats and dogs. Those studies primarily demonstrated the expected toxicity profile of BET inhibition, with most toxicity shown in the highly proliferative cell populations of the bone marrow and gastrointestinal tract. An additional toxicity observed in the rat but not dog was mammary gland atrophy in males. An additional toxicity observed in the dog but not rat was testicular degeneration. An additional toxicity finding observed in pregnant rats demonstrated embryolethality and teratogenicity. A detailed description of these toxicities is provided in Section 1.4.2 and in the Investigational Brochure. The GI and bone marrow toxicities were reversible upon discontinuation of the drug.

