The nonclinical toxicity profile was used to determine the starting dose and to develop appropriate exclusion criteria, contraception measures for male and female participants, and safety monitoring for this study. In addition to frequent complete blood counts (CBCs) and chemistry (including liver enzyme) tests, because of the potential effect of immune system repression, subjects with viral infection (Human immunodeficiency virus [HIV], Hepatitis B or C) are excluded and lymphocyte numbers are monitored regularly. Immunoglobulin levels are also followed routinely to evaluate the potential need for supplementation. Although the nonclinical in vitro and in vivo assessments have not demonstrated any cardiovascular liability, electrocardiograms (ECG) are being monitored frequently. Subjects will be evaluated frequently by physical exam; their weights are being closely monitored, and they are being assessed for the development of diarrhea or other anticipated GI symptoms. Guidelines for the management of diarrhea are provided in Section 4.5.3.

As of the data cutoff date on 21-Dec-2018, preliminary clinical data from the first-in-human CA011001 monotherapy study in subjects with advanced solid tumors have demonstrated that BMS-986158 has an acceptable toxicity profile in 81 subjects treated at all dose levels in Schedule A (0.75, 1.25, 2, 3, and 4.5 mg), Schedule B (2 and 3 mg) and Schedule C (2, 3, and 4.5 mg). All

observed toxicities in the GI or hematopoietic system reversed spontaneously or upon drug withdrawal. To date, the cumulative human safety data are consistent with the non-clinical assessment of toxicity in rats and dogs and support the continued clinical exploration of BMS-986158 for the treatment of a variety of malignancies.

Although BMS-986158 does not demonstrate evidence of genotoxicity, perturbation of cellular differentiation pathways may contribute to development of cancer. Subjects are informed of the potential risk, and are carefully evaluated by the investigators throughout the study. Subjects are counseled on appropriate contraceptive measures, while on study and for at least 3 months after the last dose of BMS-986158. Additionally, subjects are informed of the potential risks to reproductive organs and the option of sperm or egg banking discussed, if appropriate.

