- (3) Had progression or refractory disease during or after at least 1 treatment with a taxane and with an androgen pathway antagonist (eg, abiraterone or enzalutamide). Abiraterone but not enzalutamide may be continued during the study.
- (4) Detected MYC amplification in tumor cells (with or without AR amplification)

x) Part 2 only: NUT-midline carcinoma (NMC)

- (1) Adult and adolescent subjects with Fluorescence in situ hybridization (FISH)confirmed fusion of NUT with BRD3 or BRD4
- (2) Unresectable, or had progression or refractory disease during or after any line of therapy

xi) Part 2 only: Ewing sarcoma (ES)

- (1) Adult and adolescent subjects with FISH-confirmed fusion of EWS with FLI1
- (2) Had progression or refractory disease during or after at least 1L chemotherapy regimen

xii) Part 2 only: Burkitt's lymphoma/leukemia (BL)

- (1) Adult and adolescent subjects with FISH-confirmed rearrangement of MYC
- (2) Had progression or refractory disease during or after at least 1L chemotherapy regimen
- (3) Confirmed presence or absence of bone marrow involvement before enrollment.

xiii) Part 2 only: Double-hit lymphoma (DHL) or non-germinal center subtype of diffuse large B-cell lymphoma (non-GC-DLBCL)

(1) FISH-confirmed rearrangement of MYC and of BCL2 or BCL6 DHL

- (2) Had progression or refractory disease during or after at least 1 chemotherapy regimen
- (3) Confirmed presence or absence of bone marrow involvement before enrollment
- (4) IHC confirmed CD 10-, BCL6- DLBCL, or CD10-, BCL6+ and MUM1+ DLBCL. Gene expression profile may also be used to confirm a diagnosis of non-GC-DLBCL
- **xiv) Part 2 only**: adolescent subjects with malignancies harboring genetic abnormalities likely sensitive to BET inhibition who have progressive disease with no effective therapeutic options may be enrolled after discussion and agreement between the Sponsor/Medical Monitor and Investigator.
- b) Subjects with controlled, treated brain metastasis fulfilling all the following criteria may be screened: no radiographic progression for at least 2 weeks following radiation and/or surgical treatment, off steroids for at least 2 weeks, without new or progressing neurological signs or symptoms.
- c) All subjects must have at least one measurable lesion at baseline by computed tomography (CT) or magnetic resonance imaging (MRI) as per RECIST v1.1 for solid tumors or Lugano 2014 criteria for lymphomas.

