- i) For antiplatelet agents, prophylactic doses are permitted (e.g. aspirin < 300 mg daily, clopidogrel < 75 mg daily).
- j) Subject Re-enrollment: This study permits the re-enrollment of a subject that has discontinued the study as a pre-treatment failure (ie, subject has not been treated). If re-enrolled, the subject must be re-consented.
- k) Subjects with solid tumor types that are not included in the preferred target population may also be enrolled after a minimum of 2 subjects with the preferred tumor types have been enrolled at a single dose level during escalation, or during monotherapy expansion after discussion with the Sponsor/Study Director. These subjects must have progressed on or had refractory disease to at least one prior anticancer regimen, not be eligible for additional effective standard of care therapy for their disease, and must have the possibility of being positively impacted by the treatment offered in this study.
- 1) Androgen Receptor Deprivation (ARD) therapy is permitted for subjects with prostate cancer at doses defined by the investigator if the therapeutic agent is not a strong inducer or inhibitor of CYP3A4 activity.
- m) If biomarker result from the sector test is inconclusive, will repeat the test. If there is not enough tumor material, the tumor biopsy must be repeated. Subjects who have had prior tumor biopsy and analysis by conducted < 6 months prior to enrollment and have data available do not need to provide additional sample for testing at screening.

3) Previous Treatment

- a) Prior anticancer therapy treatments such as chemotherapy, radiotherapy, biological immunotherapy, or investigational agents (therapeutic or diagnostic) are permitted.
 - i) For cytotoxic agents, at least 4 weeks must have elapsed from last dose of prior cytotoxic anticancer therapy and the initiation of study drug administration.
 - **ii)** For non-cytotoxic agents, at least 4 weeks or 5 half-lives (whichever is shorter) must have elapsed from the last dose of prior non-cytotoxic anticancer therapy and the initiation of study drug administration. If 5 half-lives is shorter than 4 weeks, agreement with Sponsor/Medical Monitor is mandatory.
- b) *Not applicable; removed per Revised Protocol 03.* If subject had stem cell transplantation, the procedure must have occurred at least 3 months prior to treatment initiation (for autologous SCT) or 4 months (for allogeneic SCT) and without evidence of active graft-versus-host disease (GVHD).

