 - ii) Positive test for qualitative hepatitis C viral load (by polymerase chain reaction (PCR)

Note: Participants with positive hepatitis C antibody and negative quantitative hepatitis C by PCR are eligible. History of resolved hepatitis A virus infection is not an exclusion criterion.

- j) Not *applicable; removed per Revised Protocol 02*. NCI CTCAE v4.03 Grade 2 or higher peripheral neuropathy (sensory or motor).
- k) Any other sound medical, psychiatric and/or social reason as determined by the investigator.

- Use of strong inhibitors of CYP3A4 or P-gp within 1 week or 5 half-lives (whichever is longer) or strong inducers of CYP3A4 or P-gp within 2 weeks or 5 half-lives (whichever is longer). See Appendix 3
- m) Current uncontrolled autoimmune pneumonitis
- n) Use of non-oncology vaccines containing live virus for prevention of infectious diseases within 12 weeks prior to study treatment. The use of inactivated seasonal influenza vaccines, eg, Fluzone®, will be permitted on study without restriction.
- o) Uncontrolled endocrine disorder including thyroid disease
- p) Prior organ allograft or allogenic hematopoietic stem cell transplantation (HSCT)
 - i) Participants with active, known or suspected autoimmune disease. Note the following exceptions: Participants with: vitiligo, type I diabetes mellitus, residual hypothyroidism due to autoimmune condition only requiring hormone replacement, euthyroid participants with a history of Grave's disease (participants with suspected autoimmune thyroid disorders must be negative for thyroglobulin and thyroid peroxidase antibodies and thyroid-stimulating immunoglobulin prior to first dose of study treatment), psoriasis not requiring systemic treatment, or conditions expected not to recur in the absence of an external trigger are permitted to enroll.

2) Physical and Laboratory Test Findings

- a) Inadequate bone marrow function defined as:
 - i) Absolute neutrophil count (ANC) < 1,500 cells/mm³ for solid tumors and <1,000 cells/mm³ for hematologic malignancies
 - ii) Platelet count < 100,000 cells/mm³ for solid tumors and <75,000 cells/mm³ for hematologic malignancies
 - iii) Hemoglobin < 8 g/dL
- b) Abnormal blood coagulation parameters:
 - i) PT such that international normalized ratio (INR) is > 1.5x ULN (or > 2.5 x baseline, if a subject is on a stable dose of therapeutic warfarin) or a PTT > 1.2x upper limit of normal (ULN).
- c) Inadequate hepatic function defined as:

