4.5.1 Dose Limiting Toxicities

For the purpose of guiding dose escalation, DLTs will be defined based on incidence, intensity, and duration of AEs for which no clear alternative cause is identified. The DLT evaluation period for dose escalation in Part 1 Schedule A is 32 to 35 days (depending on the exact day of the start of Cycle 2); for Schedules B and C it is 35 days. For Part 1 Schedule A, subjects must receive at least 16 of 21 doses of BMS-986158; for Schedule B at least 17 of the 22 doses; and for Schedule C at least 12 of 15 doses to be considered DLT evaluable for dose escalation decisions. The DLT period for safety assessment of BMS-986158 and, if pursued, nivolumab combination therapy in Part 2 will be 28 days for all schedules which excludes a 7-day period for a single dose as in Cycle 1 in Part 1, to allow similar drug exposure and appropriate comparison of the safety profile between Part 1 and Part 2. For Part 2 safety assessment of the combination therapy (if pursued), subjects must receive at least 15 of 20 doses on Schedule A. If alternate schedules are explored, subjects must receive 16 of 21 doses on Schedule B, and 11 of 14 doses on Schedule C. AEs will be graded according to the NCI CTCAE v4.03. For the purpose of subject management, any AE that meets DLT criteria, regardless of the cycle in which it occurs, will lead to dose interruption. Subjects who withdraw from the study during the DLT evaluation interval for reasons other than a DLT may be replaced at the same dose level. The incidence of DLT(s) during the first cycles of treatment (the DLT evaluation period) will be used in dose escalation decisions and to define the MTD. AEs occurring after the DLT period will be considered for the purposes of defining the recommended Phase 2 dose, upon agreement between the Sponsor/ Medical Monitor and investigators, if the AEs are determined to have no clear alternative cause and are not related to disease progression.

DLT(s) will be defined as any of the following events unless a clear alternative cause is identified:

Non-Hematologic DLT:

Any of the following events will be considered a Non-Hematologic DLT:

- \geq Grade 3 Non-Hematologic toxicity, with the following exceptions.
 - ◆ ≥ Grade 3 electrolyte abnormalities that are not complicated by associated clinical AEs, are not clinically significant, last < 72 hours and either resolve spontaneously or respond to conventional medical intervention

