## **7.6 Safety**

Analyses of safety will be based on All Treated population and will be presented principally by treatment (“as treated”) and overall unless otherwise indicated. Deaths will be summarized by schedule.

Adverse events (AEs) will be coded according to the most current version of MedDRA and be graded using the NCI Common Terminology Criteria for Adverse Events (CTCAE) version 4.03. Drug-related AEs are those events with relationship to study drug “Related” as recorded on the CRF. If the relationship to study drug is missing, the AE will be considered to be drug-related.

Listing of AEs will include all enrolled subjects as well as SAEs and deaths, which are collected pretreatment. Summaries of AEs will include (1) events occurring from the first dose date to 30 days (inclusive) after the last dose of BMS-986158 monotherapy for subjects who are off study treatment and (2) all events occurring from first dose date for subjects who are still on study medication. AEs and treatment-related AEs will be tabulated by descending frequency of SOC and descending frequency of PT within each SOC, unless specified otherwise.

When reporting adverse events by CTC grade, summary tables will be provided based on events’ worst CTC grade (independently of relationship to study medication). Subjects will only be counted (1) once at the preferred term (PT) level, (2) once at the system organ class (SOC) level, and (3) once in the ‘Total subject’ row at their worst CTC grade, regardless of SOC or PT.

Unless otherwise specified, the AE summary tables will be restricted to on-treatment events regardless of the causality.

The analysis of laboratory results will be based on the All Treated population in participants with data. Laboratory results will be categorized according to NCI CTCAE (version 4.03) grade. Baseline is defined as the last non-missing measurement prior to the first dosing date and time. Summaries of laboratory results include baseline and (1) post-baseline results up to 30 days (inclusive) after the last dose of BMS-986158 monotherapy for subjects who are off study treatment and (2) all available post-baseline results for subjects who are still on study medication. Vital signs and clinical laboratory test results will be listed and summarized by treatment. Any significant physical examination findings and clinical laboratory results will be listed. ECG readings will be evaluated by the investigator and abnormalities, if present, will be listed.

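### The primary objective states an MTD for hematologic malignancies, but no hematologic subject can contribute to the MTD estimate, and the safety tables do not separate lymphoma from solid tumors

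*Protocol*

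**What the plan says.** **Objective.** Protocol Section 1.3.1 names "DLTs, MTD, and recommended Phase 2 dose (RP2D) of BMS-986158 as monotherapy for subjects with advanced solid tumors and hematologic malignancies". The synopsis and SAP Section 3.1 carry the same objective.

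**Who can enter dose finding.** In Protocol Section 3.3.1 the relevant entry is headed "Part 2 only: Double-hit lymphoma (DHL) or non-germinal center subtype of diffuse large B-cell lymphoma (non-GC-DLBCL", and Burkitt's lymphoma is likewise confined to Part 2. Criterion 2-k widens Part 1, but only this far: "Subjects with solid tumor types that are not included in the preferred target population may also be enrolled". Section 1.5 describes the 81 subjects treated by December 2018 in the same terms ("CA011001 monotherapy study in subjects with advanced solid tumors have demonstrated that"). Protocol Section 3.1.1 and SAP Section 2.1 select the MTD at the end of escalation, by isotonic regression on the accumulated DLT data.

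**Who receives the Part 2 regimen.** DHL and non-GC-DLBCL are two of the five Initial Expansion cohorts, at 5 to 9 subjects each. All cohorts receive 4.5 mg for 10 doses, then 3.75 mg. Section 3.3.2 sets the platelet limit at 100,000 "for solid tumors and <75,000 cells/mm³ for hematologic malignancies"; the neutrophil limits are 1,500 and 1,000 respectively.

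**Part 2 safety.** Section 3.1.2.1 keeps monitoring as in escalation. Enrollment may be interrupted in a tumor cohort where more than 29% have drug-related AEs requiring dose modification. Section 4.5.1 defines evaluability in Part 2 in one place: "For Part 2 safety assessment of the combination therapy (if pursued), subjects must receive at least 15 of 20 doses on Schedule A". SAP Section 7.6 says that safety "will be presented principally by treatment (“as treated”) and overall unless otherwise indicated". SAP Section 7.6.9 only lists DLTs.

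**The concern.** An MTD belongs to the population in which DLTs were counted. The objective claims it for two populations, while the eligibility criteria allow only one of them to supply data. Moving the dose to lymphoma may be reasonable, but it is an extrapolation, and no section says so.

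The assumption concerns the toxicity most likely to matter. Section 1.4.4 reports drug-related Grade 3 or 4 thrombocytopenia in 17 of 81 subjects, the most frequent severe related event. Section 4.5.1 makes Grade 4 thrombocytopenia a DLT. Lymphoma subjects may enter with lower counts. If they tolerated the regimen differently, Part 2 would be the first place in this trial to see it, yet the planned summaries combine both populations on one regimen. A study report could then state an MTD and RP2D for hematologic malignancies with neither a DLT rate nor a separate AE table behind it.

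**Working it through.** **1. The plan's own calculation.** Table 8.1-1 uses a Beta(1, 2.7) prior, so x DLTs in n evaluable subjects give Beta(1 + x, 2.7 + n − x). For 4 of 13 this is Beta(5, 11.7), with P(rate > 33%) = 36.8% and P(rate > 40%) = 18.1%, against 37% and 18% in the table. All 16 entries reproduce within rounding.

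**2. The same calculation for hematologic malignancies.** Part 1 contributes n = 0, so the posterior equals the prior: mean 27%, P(rate > 33%) = 34%, P(rate > 40%) = 25%, 95% interval 0.9% to 74.5%. This treats hematologic disease as its own stratum and borrows nothing from solid tumors. The plan states no borrowing model that would narrow it.

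**3. Size of the affected group.** Initial Expansion: 2 × 5 = 10 to 2 × 9 = 18 lymphoma subjects of 25 to 45, or 40%. In the Subsequent Expansion, if opened, three lymphoma cohorts give 15 to 27 of 70 to 126.

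**4. Dilution in a table by regimen.** With 27 solid-tumor and 18 lymphoma subjects, pooled rate = (27 × p_solid + 18 × p_lymphoma) / 45. The event rates are assumptions:

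| Solid | Lymphoma | Pooled |
|---|---|---|
| 10% | 40% | 22% |
| 10% | 50% | 26% |
| 20% | 40% | 28% |
| 20% | 50% | 32% |
| 27% | 27% | 27% |

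Pooled values of 26% and 28%, from widely different components, lie on either side of the 27% that arises when there is no difference.

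**5. What a separate summary could show.** Exact 95% limits, if all lymphoma subjects were evaluable: 5/18 = 27.8% (9.7% to 53.5%); 0/18 has an upper limit of 18.5%; 3/10 = 30% (6.7% to 65.2%). That describes one regimen. It does not estimate an MTD.

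**6. What the existing trigger covers.** More than 29% means 2 of 5 or 3 of 9. If the true rate of qualifying events is 27%, it is reached with probability 41% or 46%; at 40%, 66% or 77%; at 50%, 81% or 91%. It works within a tumor cohort, so it is not diluted. But it counts dose modifications, not DLTs; it has no time window; and its consequence is discretionary.

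**7. Text on the Part 2 DLT window, side by side.**
- Synopsis, DLT paragraph for Part 1: the Part 2 combination window matches Part 1 (32 to 35 days on Schedule A).
- Synopsis, Part 2: 28 days.
- Section 4.5.1: 28 days, in a sentence that can be read to include monotherapy, followed by a dose count for the combination only.
- Section 3.1.2.1: monotherapy monitoring as in escalation, with no window or dose count.
- SAP Section 4.1: no DLT window specific to Part 2.

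These do not settle whether DLTs are formally assessed in adult Part 2 monotherapy.

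**The case against.** The strongest reply is that the objective is one combined statement for all monotherapy. It has no formal hypothesis (Section 1.2) and is measured by AEs, SAEs, discontinuations, deaths and laboratory shifts (Section 8.3.1). Section 3.1.1 makes plain that the MTD comes from Part 1. The RP2D may also draw on AEs after the DLT period, by agreement of sponsor and investigators. Part 2 will give safety data on 10 to 18 lymphoma subjects, and by-subject listings would allow a split later. All of this stands, and it means that safety and tolerability in lymphoma can be described. It does not supply an MTD: one shared MTD would still be estimated in one population and claimed for two.

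Two stronger readings are tempting, and the documents do not support them.

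- A reader might infer that lymphoma subjects have no DLT evaluation or safety check. Monitoring continues as in escalation, any AE meeting DLT criteria interrupts dosing in any cycle, the 29% trigger runs per cohort, Section 3.1.2.4 adds a 33% discontinuation trigger per dose level, and DLTs are listed. What is missing is narrower: an evaluability definition and a clear window for adult monotherapy.
- A reader might infer from Section 1.5 that lymphoma tolerates BET inhibition worse. For another drug it reports that "Sixteen patients experienced Grade 3-4 thrombocytopenia and 3 patients had grade 3-4 neutropenia" among 37 treated: 43% (95% CI 27% to 61%), against 17/81 = 21% (13% to 31%) here. The drugs and doses differ. The 17 are drug-related while the 16 carry no attribution, and 10 of the 37 had myeloma. Grade 3 without clinically significant bleeding is not a DLT. Lower entry limits permit lower counts; they do not show less marrow reserve.

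**Conclusion.** The point holds in a limited form. No hematologic subject can inform the MTD that Section 1.3.1, the synopsis and SAP Section 3.1 state for hematologic malignancies; for that population the dose is extrapolated. The planned safety tables would dilute a difference in a group making up 10 to 18 of 25 to 45 Initial Expansion subjects, and the rules for assessing DLTs in adult Part 2 monotherapy are unclear.

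This rests on the eligibility text as written and on reading treatment in SAP Section 7.6 as the assigned regimen. The dilution figures depend on assumed event rates. Nothing here shows that the regimen is unsafe in lymphoma or that the primary objective as a whole fails; only the hematologic MTD cannot be estimated.

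**What to change.** 1. **Objective.** In Protocol Section 1.3.1, the synopsis and SAP Section 3.1, limit MTD determination to solid tumors. State that the dose is extrapolated to hematologic malignancies, where the objective is safety, tolerability and DLT incidence at the Part 2 regimen.
2. **Tables.** In SAP Sections 7.6 and 7.6.9, summarize Part 2 AEs, DLT incidence and platelet and neutrophil grade shifts separately for lymphoma and solid tumors, descriptively, with exact confidence intervals.
3. **Text.** Reconcile the two synopsis statements, Section 3.1.2.1 and Section 4.5.1 on whether DLTs are assessed in Part 2 monotherapy, and with what window and evaluability rule.

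The cost is a wording change, a few table columns and wide intervals at these sample sizes. No subjects or procedures are added, and no dose or dosing rule is proposed.
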